**Screening and Enrollment:** As part of the screening process, a brief anonymous pre-eligibility assessment may be conducted online or by phone prior to the full eligibility screening. The full eligibility screening may take place by phone, in a private room at one of the study sites (Brown University, Project Weber or The Miriam Hospital); or in a public location (coffee shop, library, etc) where the participant feels most comfortable. Participants will be asked to complete a survey assessing demographic information, sexual orientation, ethnic/racial identity, education level, history of HIV and other STDs, history of HIV testing, access to HIV and STD diagnostic and treatment services, recent sexual behavior, characteristics of recent partners, use of PEP previously and knowledge and anticipated acceptability of PrEP and other new biomedical prevention methods. The screening visit will take place in a private room at one of the study sites (Brown University, Project Weber or The Miriam Hospital); the participant can select where he feels most comfortable. Enrollment will be limited to participants who are English -speaking, HIV-uninfected, report having exchanged sex for money or drugs with another man in the past three months in RI, report at least one episode of condomless anal intercourse with an HIV-infected or unknown serostatus partner in the previous three months, who express an interest in using PrEP as an HIV prevention tool and live in the New England area. Potential participants will be asked to undergo antibody testing for HIV as well as screening for Hepatitis B infection (Hepatitis B surface antigen and antibody) and renal insufficiency (serum creatinine). Individuals will also be screened for acute HIV infection. A release of medical information will be requested upon enrollment. Only information regarding the PrEP clinic visit is requested and completion of the release is voluntary.

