## PROTECTION OF HUMAN SUBJECTS

### Potential Risks

Protected Health Information: This study will obtain data on sexual practices, sexual partners, drug use, visitation to local sex venues and attitudes regarding aspects of STIs. During the course of the study, preservation of confidentiality and safeguarding of PHI will be a paramount concern. A potential risk is breach of confidentiality and privacy.

Psychological Consequences: Another potential risk of the study is the possibility that participants could become upset, uncomfortable, or have other serious emotional responses to discussing sexual network information and risk behaviors during the study.

Risk of loss of privacy or confidentiality: Participants in Stage 2 intervention may opt to receive a study cell phone for appointment reminders and text messages. Any communication deployed via study cell phone will not contain information about the participant's health, medication or any information identifying them as a MSW. Participants can decline this phone and stop using it at any time.

Recruitment and Informed Consent: Subjects will be recruited through Project Weber as described above. Potential participants will be offered enrollment in the study by research personnel. Participants will be told that the study is being performed to help evaluate the ways in which STIs spread through the community and how infection may be prevented. Conversations will be held in closed and private areas. Participants who agree to enter the study will sign a statement of informed consent. Participants will be informed that they do not have to answer any of the questions if they choose not to.

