### Adequacy of Protection against Risks

Protected Health Information: For all components of the research plan, the study team will clearly identify themselves as being research personnel from The Miriam Hospital and Brown University. During the course of informed consent, strict confidentiality will be assured to all subjects and will be stated on the informed consent form. Only the PI and immediate study personnel performing the study will have access to PHI and other sensitive data. All data including names and identifying information will be kept behind locked

doors in locked cabinets or on password-protected Lifespan and Brown University computers. Data obtained over the web survey will be collected in a secure and encrypted format available only to research staff. Data emailed over the internet will be avoided, but if essential will be using standard encryption browser technology through the Lifespan VPN (encrypted using 'PHI' – personal health information - in the subject line, as per routine clinical practice). All persons involved in this research project will undergo human subjects and HIPAA training. In the event that confidentiality is breached, the PIs, mentoring team, and IRB will immediately be notified. All conversations with study subjects will be behind closed doors in confidential settings to address privacy.

**Psychological Consequences:** Any psychological or other mental health consequences as a result of this study will be immediately referred to the study PIs and will be addressed by the study team and by trained clinical psychologists that currently provide support services at the Immunology Center, free of charge. Participants will be able to stop the assessment or interview at any point and may discontinue their involvement in the study at any time.

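### Eligibility screening is allowed in public places, but the protocol's privacy safeguard says every conversation is held in private, with no exception

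*Protocol*

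**What the plan says.** **Where screening may take place.** The Screening and Enrollment paragraph of the Research Protocol gives three settings for the full eligibility screening: phone, a private room at a study site, "or in a public location (coffee shop, library, etc) where the participant feels most comfortable". Before that, "a brief anonymous pre-eligibility assessment may be conducted online or by phone prior to the full eligibility screening". The same paragraph later states: "The screening visit will take place in a private room at one of the study sites". Two other places widen the range of settings. Study Sites has Project Weber staff screening at the drop-in center and on routine outreach. Recruitment allows a $5 gift card for completing the eligibility survey and gives bathhouses as an example of the venues it has in mind.

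**What screening covers.** The survey described in that paragraph includes HIV and STD history and "recent sexual behavior, characteristics of recent partners, use of PEP previously and knowledge and anticipated acceptability of PrEP".

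**How privacy is protected.** Potential Risks says of the risk to personal health information: "A potential risk is breach of confidentiality and privacy", and adds that "preservation of confidentiality and safeguarding of PHI will be a paramount concern". Its Recruitment and Informed Consent paragraph says: "Conversations will be held in closed and private areas". Adequacy of Protection against Risks repeats the safeguard in universal form: "All conversations with study subjects will be behind closed doors in confidential settings to address privacy".

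**The concern.** The operating rule and the safeguard cannot both be followed when a man is screened aloud in a coffee shop. Staff who rely on Screening and Enrollment would be within that section but in breach of the two protection statements. An ethics reviewer who relies on the protection statements would conclude that such a conversation cannot occur.

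What is at stake is participant protection. The disclosures at issue are sex work with men and HIV-related sexual risk, in a group that the Certificate of Confidentiality paragraph itself treats as vulnerable. The exposure is not confined to those who enroll. A man who answers the questions and proves ineligible has made the same disclosures.

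**Working it through.** The plan gives no figure on this point and none is needed. The check is to set the passages side by side and see whether any reading makes them agree.

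| Place in the protocol | Rule on setting | Exception stated |
|---|---|---|
| Screening and Enrollment, full eligibility screening | Phone, private room, or public location | – |
| Screening and Enrollment, screening visit | Private room at a site | None |
| Study Sites, Project Weber | Drop-in center and outreach | – |
| Recruitment, screening incentive | Particular venues, bathhouses as example | – |
| Potential Risks, Recruitment and Informed Consent | Closed and private | None |
| Adequacy of Protection against Risks, Protected Health Information | Closed doors, all conversations | None |

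**Step 1. Could the safeguard cover enrolled men only?** The phrase about study subjects in Adequacy of Protection could be read that way. The parallel sentence in Potential Risks is harder to confine. It sits in the recruitment and consent paragraph, after text on offering enrollment to potential participants and before the signing of consent, so it reaches men who are not yet enrolled.

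**Step 2. Could the screening visit be a separate, later, private step?** If so, the full eligibility screening still comes first. To do its job it must establish the two behavioral criteria in the Inclusion criteria: sex exchanged with a man for money or drugs, and condomless anal sex with an HIV-infected or unknown-status partner, both within three months. The sensitive answers have then already been given. If the two are one event, the paragraph contradicts itself on location. The conflict remains either way.

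**Step 3. Does the mode of administration remove the conflict?** Screening and Enrollment and Recruitment both speak of a survey. Data management says demographic and behavioral assessments are given mainly on a tablet, with answers encrypted and sent at once to a secure server, and with paper as a back-up. Silent completion would largely meet the privacy aim. But nothing restricts screening in public to that mode, and the phone option shows that spoken screening is foreseen. The conflict is therefore conditional: it arises when the public option is used with spoken questions, and the text permits that combination.

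**Step 4. Is there an off-site safeguard elsewhere?** The screening text describes none for public places. Research Assessments confines study assessments to the three named sites, apart from a phone option for Stage 2 follow-up in exceptional circumstances, so public screening stands outside the pattern used in the rest of the study.

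**The case against.** The best case for the plan is that the public setting is optional and tied to where the participant is most at ease, in a population that Recruitment calls difficult to reach. Removing it could lose men whom the trial needs. In-person screening may also be tablet-based by default, so that little is said aloud. Both points have force. They are reasons to keep a public option in a controlled form and not simply strike it out. They do not make the unqualified safeguard true.

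A reader might also infer more than the documents support:

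- **That privacy fails at first contact.** Outreach, or the anonymous online or phone pre-assessment, may come earlier. The conflict is at the full eligibility screening.
- **That men questioned in public will under-report and be wrongly excluded.** Nothing in the documents shows this. A setting chosen by the participant could affect reporting or enrollment in either direction.
- **That participants were promised closed settings.** The two sentences are protocol text, and the consent form is not available here. The protocol says only that subjects will be assured strict confidentiality.
- **That eligibility questions will in fact be read aloud in coffee shops.** The mode of in-person screening is not stated.

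**Conclusion.** The contradiction is real and rests on the text alone. Public and outreach screening is permitted, the closed-door safeguard has no exception, and no reading reconciles the two when questions are spoken. In that case the stated protection against a breach of confidentiality is not delivered, for men who enroll and for men who screen out.

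Its size cannot be given as a number. The documents report neither the share expected to be screened in public nor the number screened for the 130 planned enrollments, and any assumed share would be a guess. The conclusion does not depend on one. It does depend on the public option being used with spoken questions, which the protocol permits but does not require.

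The point has no bearing on randomization, endpoints, sample size or analysis. It is worth correcting because the safeguard concerns a risk that the protocol treats as paramount, and because the correction is cheap.

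**What to change.** Amend Study Sites (Project Weber), Recruitment, Screening and Enrollment, Potential Risks (Recruitment and Informed Consent) and Adequacy of Protection against Risks so that all state one rule:

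1. Spoken eligibility questions are asked only by phone or in a private room.
2. Any screening in a public place or outreach venue is limited to silent self-completion on the encrypted tablet already described under Data management. No sensitive question and no eligibility result is spoken aloud there.
3. The sentence on all conversations in Adequacy of Protection is qualified to match, so that it describes what staff will actually do, including by phone.

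The paper back-up under Data management should be checked against point 2 at the same time.

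Deleting only the coffee-shop wording would not be enough, because the outreach and venue screening in Study Sites and Recruitment would still conflict with the safeguard.

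The cost is one wording amendment, with no new data system. The downside is small: some men who prefer to meet in public would have to complete the survey themselves or be screened by phone.

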**Inclusion criteria:**

- 18 years of age or older
- Assigned male at birth
- Report having exchanged sex with another man for money or drugs in the past three months
- Report behavioral risk for HIV infection, consistent with Centers for Disease Control and Prevention guidelines for prescribing PrEP: condomless anal intercourse with at least one HIV-infected or unknown serostatus partner in the past three months
- HIV-negative by antibody test \*Stage 2
- Able to understand and speak English, for consenting and counseling
- Lives in the New England area
- Willing to initiate PrEP

**Exclusion criteria:**

- Unable to provide informed consent, including as a result of severe mental illness requiring immediate treatment or mental illness limiting the ability to participate
- HIV Positive at baseline
- Infected with Hepatitis B or diagnosed with renal insufficiency (glomerular filtration rate < 50) \*Stage 2
- History of or current medical conditions that would preclude taking Truvada for PrEP \*Stage 2
- Currently taking Truvada for PrEP

Sample size: We expect to recruit 130 participants for the pilot RCT (Specific Aim 1).

## PROTECTION OF HUMAN SUBJECTS

### Potential Risks

Protected Health Information: This study will obtain data on sexual practices, sexual partners, drug use, visitation to local sex venues and attitudes regarding aspects of STIs. During the course of the study, preservation of confidentiality and safeguarding of PHI will be a paramount concern. A potential risk is breach of confidentiality and privacy.

Psychological Consequences: Another potential risk of the study is the possibility that participants could become upset, uncomfortable, or have other serious emotional responses to discussing sexual network information and risk behaviors during the study.

Risk of loss of privacy or confidentiality: Participants in Stage 2 intervention may opt to receive a study cell phone for appointment reminders and text messages. Any communication deployed via study cell phone will not contain information about the participant's health, medication or any information identifying them as a MSW. Participants can decline this phone and stop using it at any time.

Recruitment and Informed Consent: Subjects will be recruited through Project Weber as described above. Potential participants will be offered enrollment in the study by research personnel. Participants will be told that the study is being performed to help evaluate the ways in which STIs spread through the community and how infection may be prevented. Conversations will be held in closed and private areas. Participants who agree to enter the study will sign a statement of informed consent. Participants will be informed that they do not have to answer any of the questions if they choose not to.

Certificate of Confidentiality: This research specifically targets a vulnerable population, men who have sex with men in exchange for money. We will take every available step to minimize the risk of identifying/linking data being subpoenaed, stolen, or inadvertently released. We will request a Certificate of Confidentiality from the NIH prior to enrolling participants. As noted on the NIH website (<http://grants.nih.gov/grants/policy/COC/faqs.htm#187>), a Certificate of Confidentiality will help the research team "...avoid compelled 'involuntary disclosure' (e.g., subpoenas) of names and other identifying information about any individual who participates as a research subject (i.e., about whom the investigator maintains identifying information) during any time the Certificate is in effect." We have applied for and received Certificates of Confidentiality for other NIH-funded research projects, and given the sensitive nature of the data collected for this project, do not foresee difficulty securing one for this study.

### Adequacy of Protection against Risks

Protected Health Information: For all components of the research plan, the study team will clearly identify themselves as being research personnel from The Miriam Hospital and Brown University. During the course of informed consent, strict confidentiality will be assured to all subjects and will be stated on the informed consent form. Only the PI and immediate study personnel performing the study will have access to PHI and other sensitive data. All data including names and identifying information will be kept behind locked

doors in locked cabinets or on password-protected Lifespan and Brown University computers. Data obtained over the web survey will be collected in a secure and encrypted format available only to research staff. Data emailed over the internet will be avoided, but if essential will be using standard encryption browser technology through the Lifespan VPN (encrypted using 'PHI' – personal health information - in the subject line, as per routine clinical practice). All persons involved in this research project will undergo human subjects and HIPAA training. In the event that confidentiality is breached, the PIs, mentoring team, and IRB will immediately be notified. All conversations with study subjects will be behind closed doors in confidential settings to address privacy.

**Psychological Consequences:** Any psychological or other mental health consequences as a result of this study will be immediately referred to the study PIs and will be addressed by the study team and by trained clinical psychologists that currently provide support services at the Immunology Center, free of charge. Participants will be able to stop the assessment or interview at any point and may discontinue their involvement in the study at any time.

**Risk of loss of privacy or confidentiality:** Study cell phones are issued by AT&T through Brown University. Individual study cell phones cannot be traced back to research participants by name. Study phones are registered by study ID and identified as the Center for Health Equity Research (at Brown University). Daily adherence SMS text messages are deployed utilizing a web-based data management system which is password protected and only trained study personnel can access. If participants who use study cell phone agree to receive appointment reminders via this device, the phone number is recorded the link file containing contact information. This file is password protected and can only be accessed by trained study personnel.

#### **Additional Protections for Children**

The prospective component of this proposal will only enroll individuals aged 18 years or older and is not pertinent to children.

#### **Data and Safety Monitoring Plan**

We have identified [name] and [name] as two individuals qualified to assist us in the oversight of participant safety and the monitoring of any unforeseen events during this study. Drs. [name] and [name] are not directly involved in our study and can provide unbiased input and advice. Both are experienced in working with both HIV-infected and HIV at-risk individuals. We will provide Drs. [name] and [name] with a status summary of research activities via email for review on at least a half-yearly basis. In addition, Drs. [name] and [name] will be available on an ad-hoc basis as necessary for us to discuss any issues that may arise.

#### **Potential Benefits of the Proposed Research**

There will be no direct benefit from participating in this study to the participating subjects. Subjects will receive education and counseling to reduce risky behaviors. The public health benefits and knowledge gained during this study will lead to a better understanding of PrEP uptake and adherence among male sex workers.

### **TIMELINE**

The expected timeline of the study is three years. Review and updates will be provided to the IRB as necessary.

Statistical Analysis Plan

September 15, 2015

Optimizing PrEP Uptake & Adherence Among Male Sex Workers (MSW)
Using a 2-stage Randomization Design
(NCT03086057)

Specific Aim 2: Pilot RCT. Initially, the distribution of all variables will be assessed, as will the autocorrelations across time between all study variables and the primary outcomes. Dependent variables will be examined to determine which distributional models are most appropriate for subsequent statistical procedures. We will examine the equivalence of the random assignment of groups with regards to key baseline characteristics, including socio-demographics and sexual risk-related variables. In the unlikely event that randomization does not work to balance these characteristics at baseline, we will assess whether baseline differences may account for differences in outcomes. Attrition effects will be evaluated by testing whether systematic differences exist between those participants who complete the research versus those who drop out. In this way, we can determine the nature of the potential bias introduced by attrition from the study.

Primary Analysis. The primary analysis for Stage 1 will compare PrEP initiation at 1-month post Stage 1 randomization between the study arms. For stage 2, the primary analysis will compare adherence (defined by percent of drug in blood) at the 3 and 6 month visits between the study arms. Changes in self-reported adherence, sexual behavior adjustment and substance use will also be examined. Moreover, group differences in number of PrEP clinic appointments kept will be compared. All analyses will use two-tailed tests of significance, with significance at alpha = 0.05. We will use generalized linear models (GLM) with properly-chosen link functions to analyze longitudinal data for each analysis. The GLMs will be estimated using generalized estimating equations with robust standard error estimates (GEE)^{67,68}, which provides an extension of regression analysis to the case of correlated or repeated observations and allows for inclusion of both categorical and count dependent variables and for appropriate modeling of covariance structures when observations are correlated across time. We will follow an intent-to-treat model, analyzing participants in the study arm to which they were assigned, regardless of fidelity to assigned group.

Mediation analysis. If the intervention does achieve adherence in significantly greater magnitude than the comparison condition, we will preliminarily explore the extent to which this relationship works through several possible mediators, as detailed above. A multiple mediator analysis, which examines the effects of the potential mediators simultaneously in the same statistical model and is consistent with Baron and Kenny as updated by Kraemer^{69,70}, will be used to quantify the magnitude of the mediation.

Moderator analysis. To preliminarily explore effect modification, we will add interaction terms one-by-one for the intervention condition and the potential moderators. Significant or large interaction terms suggest that the effects of the intervention differ for different subgroups, as defined by the moderators.

For the mediation and moderator analyses, given the aim of the study is to pilot the intervention to assess participant acceptability and determine feasibility of all study procedures, we will assess whether the intervention impacts the hypothesized mediators and moderators in the expected direction per our conceptual model, not rely on statistical significance.

Power and Sample Size Considerations. As a pilot study, the primary emphasis is on feasibility of the two arms and hence power is limited; and to find statistical significance, the effect sizes would need to be large. However, the number of repeated measures does increase power for the longitudinal analyses. For stage 1, proportion of participants in each condition who initiate PrEP, with a two-tailed p-value of 0.05, and 53 participants per arm, we would need at least a 30 percentage point difference across the two conditions (e.g., if 20% of the comparison arm and 50% of the intervention arm initiated PrEP) to achieve 80% power. For stage 2, percent adherence since the last visit will be assessed yielding 3 repeated blood-drug levels across baseline, 3, and 6. With a two-tailed p-value of 0.05, group sample sizes of 22 participants per arm, assuming a correlation of 0.80 between repeated adherence measures and with up to 10% attrition there will be greater than 80% power to detect in excess of a medium effect size difference (approximately 10% in the slope) between the intervention and comparison groups. For categorical outcomes (e.g. percent of patients in each condition achieving at least 90% adherence via blood drug levels), with a two-tailed p-value of 0.05, the three repeated measures, and 22 patients per arm, we would need at least a 25 percentage point difference across the two conditions (e.g., if 50% of the comparison arm and 75% of the intervention arm had at least 90% adherence) to achieve 80% power.

Missing Data. We will assess for patterns of missing data, which are expected to be low as the study utilizes A-CASI. We will explore strategies for imputing missing data based on patterns of missingness and apply appropriate techniques, applying sensitivity analysis to determine the optimal method of handling the missingness⁷¹⁻⁷³.
